9.4.3. Secondary Endpoint(s)

The secondary endpoint(s) of the trial are:

- Combined assessment of change in ALSFRS-R total score, time to dependence on assisted ventilation (invasive or non-invasive), and survival time up to Week 24.
 - Dependence on assisted ventilation is defined as patients using non-invasive or invasive ventilation for ≥ 22 hours per day for ≥ 10 consecutive days
 - Patients with dependence on assisted ventilation are ranked lower than those with the largest drops in ALSFRS-R scores but higher than those who have died
- Change from baseline to Week 24 in the percent predicted FVC
- Change from baseline to Week 24 in the ALSAQ-40 total score
- Change from baseline to Week 24 in hand grip strength (average of both hands)

The analyses of the secondary endpoints are as follows:

The estimand of the first secondary endpoint of combined assessment of change in ALSFRS-R total score, time to dependence on assisted ventilation, and survival time up to Week 24 is the Mann-Whitney probability for more favorable status at week 24 for reldesemtiv than placebo in the paradigm where deaths have the worst ranks, patients with dependence on assisted ventilation have the next worst ranks, and the more favorable changes from baseline at week 24 in ALSFRS total score have the better ranks using a joint-rank test in the FAS (Berry 2013). The detailed ranking and imputation methods for missing data will be provided in the SAP. The joint ranks will be determined based on the combined assessments and analyzed using a stratified Wilcoxon test that compares the ranks between reldesemtiv and placebo groups while adjusting for baseline riluzole use status and baseline edaravone use status. Stratified Mann-Whitney test statistics as well as the p-value will be presented. Sensitivity analyses and associated details will be included in the SAP.

Analyses for the remaining other secondary endpoints will be performed using a MMRM with the following model terms: treatment group, baseline ALSFRS-R total score, visit, riluzole use status at baseline, edaravone use status at baseline as well as baseline-by-visit and treatment group-by-visit interactions, using an unstructured variance-covariance matrix.

To support the analysis results of the key secondary endpoints, the joint rank analyses will also be performed for change from baseline up to Week 24 in the percent predicted FVC, and for change from baseline up to Week 24 in the ALSAQ-40 total score.

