**Methodology:**

This is a Phase 3, double-blind, randomized, placebo-controlled trial of reldesemtiv in patients aged 18 to 80 with ALS. The screening and qualification period for the trial will be no more than 21 days in duration. Approximately 555 eligible ALS patients will be randomized (2:1) to receive the following dose of reldesemtiv or placebo (stratified by riluzole use and edaravone use at baseline) for the first 24 weeks (double-blind placebo-controlled period):

- 300 mg reldesemtiv twice a day for a 600 mg total daily dose (TDD)
- Placebo twice daily

At the end of the 24-week double-blind, placebo-controlled period, patients will transition to the active drug period, where all patients will receive the following dose of reldesemtiv for the next 24 weeks:

- 300 mg reldesemtiv twice a day for a 600 mg TDD for patients who were not down titrated during the 24 weeks of blinded dosing
- 150 mg reldesemtiv twice a day for a 300 mg TDD for patients who were down titrated for any reason during the 24 weeks of blinded dosing

For the entire 48 weeks of dosing, patients and sites shall remain blinded to the randomized treatment assignment patients received during the first 24 weeks.

Study drug should be taken twice daily, morning and afternoon (at least 8 hours apart) and should be taken either with or within the 2-hour period following food.

For patients who complete Week 48 and want to enter the open label extension (OLE), they will not have the follow-up visit; instead, they will enter the OLE on the same day as their Week 48 visit. If the patient does not want to enter the OLE, or if the OLE has not yet been approved at the site, the follow-up visit will take place.

**Number of Subjects (planned and analyzed):** Approximately 740 patients will be screened in order to randomize/enroll approximately 555 patients, such that approximately 444 evaluable patients complete the 24-week of double-blind placebo-controlled period of the trial.

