### 4.3. Sample Size Considerations

#### 4.3.1. Sample Size Justifications

With a 2:1 randomization ratio to reldesemtiv and placebo groups, respectively, an initial sample size of approximately 555 patients is required to achieve at least 90% power to detect a 1.8 point treatment difference between reldesemtiv and placebo in the change from baseline to Week 24 in ALSFRS-R total score. This calculation is based on a two-sample t-test with two-sided alpha at 0.05 level, a common standard deviation of 5.5 points, and accounting for data missing and early treatment termination.

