sample size, the CDL method could allow the final analysis to include all data before and after the interim look without inflating the type-1 error. This interim analysis will spend a very small 2-sided alpha of 0.0001 for the primary endpoint as well as all individual secondary endpoints. The DMC is also expected to recommend stopping this trial due to superiority if a two-sided p-value is  $\leq$  alpha of 0.0001 for the primary endpoint as well as all individual secondary endpoints. Therefore, the significance level of 2-sided alpha of 0.0499 would be used for the final analyses for the primary endpoint and all individual secondary endpoints to control familywise error rate at overall alpha of 0.05.

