## 8.6. Analysis of the Primary Efficacy Endpoint

### 8.6.1. Primary Efficacy Analysis

The primary efficacy endpoint of the trial is the change from baseline to Week 24 in ALSFRS-R total score. The estimand of the primary efficacy endpoint is the difference in the mean changes from baseline to Week 24 in ALSFRS-R total score between patients randomized to placebo and those randomized to reldesemtiv in the FAS.

The analysis for the primary efficacy endpoint will be conducted using a mixed model for repeated measures (MMRM) based on a restricted maximum likelihood method (SAS® PROC MIXED default). The model terms will include treatment group, baseline ALSFRS-R total score, visit, riluzole use at baseline, edaravone use at baseline as well as baseline-by-visit and treatment group-by-visit interactions. In addition, other baseline covariates identified by stepwise selection in a regression model will also be included in the model if they are key predictor variables for the change from baseline to Week 24 in ALSFRS-R total score. The regression model used to identify baseline covariates will include change from baseline to Week 24 in ALSFRS-R total score as response variable and pre-study disease progression rate, age and baseline percent predicted FVC as model terms. The stepwise selection process with significance at 0.25 level for a variable to be entered to the model and with significance at 0.1 level for a variable to remain in the model will be used. The best-fit model according to AIC will be selected. The evaluation will be performed based on the blinded data before the database lock. An unstructured variance-covariance matrix will be used for the model. Observed data collected up to Week 24 in the FAS will be included in the model.

Prior to applying the MMRM, multiple imputation with fifty invocations under the MAR paradigm will be performed to impute missing data (see [Section 8.6.1.1](#) for imputation method).

Least squares mean (LSM), LSM difference and the corresponding standard error, 95% CI and p-value will be presented. The components used to derive main estimator of the primary analysis are shown in [Table 4](#).

Sensitivity analyses will be conducted to support the robustness of conclusions based on the primary analysis results. See [Section 8.6.2](#) for sensitivity analyses.

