- For patients who discontinued early, comparison is based on the last time-point measurements that are both available for the patients in pairs.
- If it is not possible to assign either patient as having the better outcome, then the score assigned to the pair is 0.

For each patient, the assigned scores (+1, -1 or 0) from the pairwise comparisons with all others will be summed, then all patients in the FAS will be ranked according to their summed scores to create a rank score from 1 for the lowest possible summed score to N (total number of patients in the analysis population) for the highest possible summed score. If ties occur, each of the tied summed scores will be assigned the average of the ranks the tied summed scores would have if there were no ties.

A stratified Wilcoxon test will be applied to compare the standardized joint ranks between reldesemtiv and placebo groups (as ranks divided by pooled group sample size plus one) adjusting for baseline riluzole use and baseline edaravone use. The win probability, win ratio, van Elteren (or stratified Wilcoxon) test statistic, and p-value will be presented.

In the event that mortality rate up to week 24 is higher than expected, the first secondary endpoint may be considered as the primary efficacy endpoint before database lock for the Week 24 primary analysis.

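### The first secondary joint-rank test is valid but adjusts only for riluzole and edaravone use, giving up precision from baseline covariates that the primary analysis uses or may use

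*SAP*

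**What the plan says.** **The joint-rank test.** SAP 8.7.1 ranks deaths worst, then patients dependent on ventilation, then everyone else by decline in ALSFRS-R. The standardised joint ranks are compared between arms ("as ranks divided by pooled group sample size plus one) adjusting for baseline riluzole use and baseline edaravone use"). Protocol 9.4.3 agrees: "adjusting for baseline riluzole use status and baseline edaravone use status". The sample code in SAP 12.5 carries strata, treatment and rank, and no covariate. Sensitivity Estimators 7 to 10 in SAP 8.7.2 all reuse the 8.7.1 method. SAP 5.2 adds stratification by inclusion in the second interim analysis, and ranking separately by cohort, only if the sample size is increased.

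**The primary model.** SAP 8.6.1 fixes baseline ALSFRS-R and its visit interaction in the MMRM. It then screens further covariates by stepwise regression on blinded data, with "pre-study disease progression rate, age and baseline percent predicted FVC as model terms". Those retained enter the primary model.

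**The imputation.** SAP 8.7.1.1 refers to 8.6.1.1, whose model uses earlier ALSFRS-R values including baseline, together with the selected covariates.

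**The endpoint's role.** In SAP 8.5, failure at Step 2 ends testing, so FVC, ALSAQ-40 and handgrip are not tested. SAP 8.7.1 also allows this endpoint to be made primary before lock if mortality is higher than expected. No power is stated for it.

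**The concern.** Among survivors not dependent on ventilation, the joint rank orders the same ALSFRS-R change that the primary analyses. Any covariate retained by the blinded selection has been retained because it predicts that change. The plan therefore uses it to sharpen the Step 1 comparison and to fill in missing scores, then leaves it out of the Step 2 comparison. It gives no reason for the difference.

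Use in the imputation model does not recover this precision. Imputation affects the values assigned to patients with missing scores. The variance of the between-arm comparison is still computed as though nothing prognostic were known beyond the two drug-use factors.

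At stake is the chance of passing Step 2 when the drug works, and with it the chance to test three further endpoints. If this endpoint were made primary, the trial's main test would lack the baseline adjustment now planned for the primary.

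**Working it through.** **Inputs from the documents**
- Test, alpha and SD (SAP 4.3.1): "two-sample t-test with two-sided alpha at 0.05 level, a common standard deviation of 5.5 points"
- Power and effect (SAP 4.3.1): "at least 90% power to detect a 1.8 point treatment difference"
- Allocation (SAP 4.3.1): "With a 2:1 randomization ratio to reldesemtiv and placebo groups"
- Numbers (SAP technical summary): "randomize/enroll approximately 555 patients, such that approximately 444 evaluable patients complete", a loss of 1 − 444/555 = 20%
- Final alpha (SAP 5.1): "2-sided alpha of 0.0499 would be used for the final analyses for the primary endpoint and all individual secondary endpoints". SAP 8.5 gives 0.05 for Step 2. I used 0.0499; the difference is negligible for power.

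**Assumptions, not in the documents:** R², the share of outcome (or rank) variance explained by the covariates; 5% deaths and 2% ventilated, both unaffected by treatment; and the primary's 1.8-point shift applied to the joint rank.

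**1. Reproduce the stated sample size.** Placebo n = (1 + 1/2) × (1.960 + 1.282)² × 5.5²/1.8² = 1.5 × 10.51 × 9.336 = 147.2, so 148. The total is 3 × 148 = 444, and 444/0.80 = 555. Exact t-test power is 0.900 at 444 and 0.952 at 555. The plan's figure reproduces.

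**2. Planned joint-rank power with no deaths.** The shift corresponds to a Mann-Whitney probability of Φ(1.8/(5.5√2)) = 0.592. With Wilcoxon efficiency 3/π, the expected z is (1.8/5.5) × √(3/π) / √(1/n_placebo + 1/n_active).
- N = 444 (148 and 296): 0.3273 × 0.9772/0.1007 = 3.18. Power = Φ(3.18 − 1.96) = 0.888.
- N = 555 (185 and 370): 0.3273 × 0.9772/0.0900 = 3.55. Power = 0.944.

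**3. Adjusted power with no deaths.** Adjustment multiplies the test variance by (1 − R²), so the expected z is divided by √(1 − R²).

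| R² | Power, N = 444 | Gain (points) | Power, N = 555 | Gain (points) |
|---|---|---|---|---|
| 0 | 0.888 | 0 | 0.944 | 0 |
| 0.05 | 0.903 | 1.5 | 0.954 | 1.0 |
| 0.10 | 0.917 | 2.9 | 0.963 | 1.9 |
| 0.20 | 0.944 | 5.6 | 0.978 | 3.4 |

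Put as patients, R² = 0.10 at N = 444 is worth 444/0.90 = 493 unadjusted, or 49 more.

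**4. With deaths and ventilation ranked worst (simulation).** With 5% deaths and 2% ventilated, the gains at R² of 0, 5, 10 and 20% were about 0, 1.5, 3 and 6 points at N = 444, and about 0, 2, 2 and 4 points at N = 555. The smallest of these are close to simulation noise.

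A second simulation used four riluzole-by-edaravone strata, 5% deaths, no ventilation tier, and a prognostic score that also predicted death:

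| R² | N = 444, planned → adjusted | N = 555, planned → adjusted |
|---|---|---|
| 0 | 0.813 → 0.809 | 0.890 → 0.884 |
| 0.05 | 0.804 → 0.830 | 0.888 → 0.902 |
| 0.10 | 0.809 → 0.850 | 0.887 → 0.920 |
| 0.20 | 0.811 → 0.883 | 0.893 → 0.947 |

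These gains are mostly larger, as expected when the covariates predict the worst tiers as well as functional change.

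**5. Type I error.** In the second simulation, rejection under the null was 0.043 to 0.056 for the planned test and 0.041 to 0.061 for the adjusted one. Each estimate rests on 2,000 runs (standard error about 0.005).

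**The case against.** The planned test is pre-specified, stratifies on the two randomization factors, and is the same in the protocol, the SAP text and the sample code. Its result can be interpreted without any change. That stands: this is not an error.

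Three stronger readings are tempting, and the documents do not support them.
- **That the prognostic covariates play no part in the joint-rank analysis.** They enter through the imputation of missing ALSFRS-R, and the ranked quantity is itself a change from baseline. What is missing is adjustment of the comparison.
- **That all four covariates are already in the primary model.** Only baseline ALSFRS-R is certain. Progression rate, age and FVC are candidates, and the selection may keep none of them.
- **That a gain of several points is assured.** Because the ranks already use change from baseline, baseline ALSFRS-R alone may add little, and at R² = 0 there is no gain. Also, 444 is the number expected to complete 24 weeks. The analysis uses the FAS with imputation, so the number ranked is nearer 555, where gains are generally smaller. Imputed scores do not carry full information, so the truth lies between the two columns.

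Two further limits stand. The simulations included neither multiple imputation nor covariate selection from the same pooled data, so near-nominal type I error is shown for a simpler procedure. The selection should do no harm in principle: it is blind to arm, so under the null of no effect in any patient it would pick the same covariates whatever the allocation. Second, a rank ANCOVA on residuals is mainly a test. Reporting an adjusted Mann-Whitney probability needs a randomization-based estimator, which must be named.

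**Conclusion.** The concern holds as one of efficiency. The joint-rank test uses only the two drug-use factors, plus interim cohort if the sample size is increased, while covariates used or eligible for the primary are left out of the comparison.

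Under the primary's planning shift, 5% deaths and 2% ventilated, the power given up is about 0 points at R² = 0, 1.5 to 2 at 5%, 2 to 3 at 10%, and 4 to 6 at 20%, over N = 444 to 555. It could be larger if the covariates also predict death. If they predict nothing, adjustment costs at most a fraction of a point.

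A reader might infer that the Step 2 test is biased or fails to control type I error. Nothing in the documents supports that. The change is worth making because the baseline data are already collected, Step 2 controls access to three further endpoints, and this endpoint may be made primary.

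**What to change.** Before unblinding, amend SAP 8.7.1 and 12.5 and protocol 9.4.3 as follows.
- **Method:** analyse the standardised joint ranks by stratified randomization-based nonparametric ANCOVA. The strata are riluzole and edaravone use, plus interim cohort if the sample size is increased, keeping the cohort-separate ranking of SAP 5.2.
- **Covariates:** baseline ALSFRS-R and whichever covariates the blinded selection keeps for the primary, with no separate selection for this endpoint.
- **Reporting:** the adjusted Mann-Whitney probability with its standard error, pooled over the 50 imputations by Rubin's rules. The Wilson-Hilferty pooling in SAP 12.5 then serves only the unadjusted test.
- **Second interim:** use the same method for this endpoint, and have the interim analysis plan state the covariate set for that look.
- **Sensitivity:** keep the unadjusted van Elteren test. State which version applies to Estimators 7 to 10 and to the subgroup and exploratory joint-rank analyses, all of which rely on 8.7.1.

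The cost is modest extra programming and alignment of the SAP, protocol and interim analysis plan. No new data or visits are needed. If the sponsor prefers not to change the confirmatory test, the adjusted analysis should at least be pre-specified as supportive, although that would not recover power at Step 2.

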9.2. Sample Size Determination

With a 2:1 randomization ratio to reldesemtiv and placebo groups, respectively, a sample size of approximately 555 patients is required to achieve at least 90% power to detect a 1.8 point treatment difference between reldesemtiv and placebo in the change from baseline to Week 24 in ALSFRS-R total score. This calculation is based on a two-sample t-test with two-sided alpha at 0.05 level, a common standard deviation (SD) of 5.5 points, and accounting for missing data and early treatment termination.

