9.4.1.1. Multiplicity Adjustment

The null hypothesis for the primary and secondary efficacy variables in the FAS will be tested in the pre-specified order using a closed testing procedure. The first secondary endpoint is the combined assessment of change in ALSFRS-R total score, time to dependence on assisted ventilation (use non-invasive or invasive ventilation for ≥ 22 hours per day for ≥ 10 consecutive days), and survival time up to Week 24. The primary endpoint will be tested first, and if this comparison between the two treatments is statistically significant, then the first secondary endpoint will be tested. The pre-specified order of the rest of the secondary efficacy endpoints will be provided in the SAP. This procedure will maintain the family-wise error rate at 5% for all hypotheses tested in a confirmatory sense.

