9.4.2. Primary Endpoint

The primary endpoint of the trial is the change from baseline to Week 24 in ALSFRS-R total score. The primary estimand is the difference in the mean changes from baseline to Week 24 in ALSFRS-R total score between patients randomized to placebo and those randomized to reldesemtiv during the placebo-controlled double-blind treatment in the full analysis set.

The primary analysis (main estimator) of the primary endpoint is as follows:

The primary endpoint will be analyzed using a MMRM based on a restricted maximum likelihood method (SAS® PROC MIXED default). The model terms will include treatment group, baseline ALSFRS-R total score, visit, riluzole use status at baseline, edaravone use status at baseline as well as baseline-by-visit and treatment group-by-visit interactions. An unstructured variance-covariance matrix will be used in the model. Additional important baseline covariates may be included to the primary analysis model if they are key predictor variables for the change from baseline to Week 24 in ALSFRS-R total score. Details of the selection procedure for the potential baseline covariates will be pre-specified in the SAP. The selection of the potential baseline covariates will be performed before the database lock.

Prior to applying the MMRM, missing data will be imputed using the multiple imputation procedure (Rubin 1987) for the primary analysis, and the estimates from each imputed dataset will be combined into one set of overall estimates using the SAS® PROC MIANALYZE procedure. The extent of missing data and the pattern of missing data reasons will be tabulated. Imputation details will be pre-specified in the SAP. Least square means (LSM), LSM difference and the corresponding standard errors, 95% CI and p-values will be presented.

Sensitivity analyses will be conducted to support the robustness of the primary analysis results. Using the ANCOVA model with the MAR-based multiple imputation for all missing ALSFRS-R assessments as the base model, the tipping point analyses will be conducted having the imputed values for the deaths successively worse only for the reldesemtiv treatment, while maintaining the MAR-based imputed values for the placebo treatment. Another sensitivity analysis will be to repeat the ANCOVA base model with missing ALSFRS-R assessments imputed as if the reldesemtiv patients were in the placebo arm. Other sensitivity analyses and the details will be included in the SAP.

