## 8.5. Multiple Comparisons and Multiplicity

The null hypothesis for the primary and secondary efficacy endpoints will be tested in a prespecified order using a closed testing procedure. This procedure will maintain the family-wise error rate at two-sided significance level of 0.0499 for all primary and secondary hypotheses tested in a confirmatory sense. The testing steps are described as follows:

- Step 1: The null hypothesis for the primary endpoint  $H_{01}$  is that there is no treatment difference in the change from baseline to Week 24 in ALSFRS-R total score between patients randomized to placebo and those randomized to reldesemtiv in the FAS. The hypothesis will be tested at the two-sided significance level of 0.0499. If this hypothesis is rejected, testing will proceed to Step 2; otherwise testing will stop.
- Step 2: The null hypotheses for the first secondary endpoint  $H_{02}$  is that the Mann-Whitney probability of a more favorable status in reldesemtiv or placebo group in the FAS is 0.5. The status is quantified by joint ranks based on the combined assessment of change in ALSFRS-R total score, time to onset of respiratory insufficiency, and survival time up to Week 24. The hypotheses will be tested at the two-sided significance level of 0.05. If this hypothesis is rejected, testing will proceed to Step 3; otherwise testing will stop.
- Step 3: The null hypotheses  $H_{03}$  is that there is no treatment difference in change from baseline to Week 24 in the percent predicted FVC between patients randomized to placebo and those randomized to reldesemtiv in the FAS. The hypotheses will be tested at the two-sided significance level of 0.05. If this hypothesis is rejected, testing will proceed to Step 4; otherwise testing will stop.
- Step 4: The null hypotheses  $H_{04}$  is that there is no treatment difference in change from baseline to Week 24 in the ALSAQ-40 total score between patients randomized to placebo and those randomized to reldesemtiv in the FAS. The hypotheses will be tested at the two-sided significance level of 0.05. If this hypothesis is rejected, testing will proceed to Step 5; otherwise testing will stop.

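### SAP 8.7.1 lets the joint-rank endpoint replace the ALSFRS-R primary on an undefined mortality trigger, contrary to the protocol's fixed primary and testing order

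*SAP*

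**What the plan says.** Protocol 9.4.2 fixes the primary: "The primary endpoint of the trial is the change from baseline to Week 24 in ALSFRS-R total score". Protocol 9.1 states the primary null hypothesis on the same variable. SAP 8.6.1 agrees: "The primary efficacy endpoint of the trial is the change from baseline to Week 24 in ALSFRS-R total score".

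The testing order is also fixed. Protocol 9.4.1.1 says "The primary endpoint will be tested first, and if this comparison between the two treatments is statistically significant", and only then is the joint-rank endpoint (death, then dependence on assisted ventilation, then ALSFRS-R change) tested. In SAP 8.5, Step 1 is ALSFRS-R change: "The hypothesis will be tested at the two-sided significance level of 0.0499". It continues: "If this hypothesis is rejected, testing will proceed to Step 2; otherwise testing will stop".

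The last paragraph of SAP 8.7.1 departs from this. "In the event that mortality rate up to week 24 is higher than expected", it says, "the first secondary endpoint may be considered as the primary efficacy endpoint before database lock for the Week 24 primary analysis". The protocol contains no such option.

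**The concern.** A fixed sequence controls error because the first hypothesis is settled before anyone can know which endpoint looks better. The clause makes that first hypothesis discretionary. With no expected rate in either document, any observed mortality could be called high, and the permissive wording leaves the choice open even then.

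The only time limit is database lock. The one lock that Protocol 9.4.1.2 describes comes after 48 weeks of treatment and safety follow-up, so the text allows the decision to follow both planned interim analyses. What is at stake is whether a positive result can be defended as pre-specified, and whether the trial is sized for the endpoint it would be judged on.

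**Working it through.** **1. What the clause leaves open.**

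| Needed for a pre-specified switch | Protocol | SAP |
|---|---|---|
| Expected Week 24 mortality or threshold | none | none |
| Who decides | none | none |
| Pooled, blinded mortality required | none | not stated in 8.7.1 (8.6.1 does require blinded data for covariate selection) |
| Testing order after a switch | none | none; 8.5 gives only the ALSFRS-R-first order |

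**2. Reproducing the sample size.** Protocol 9.2 states that "a sample size of approximately 555 patients is required to achieve at least 90% power to detect a 1.8 point treatment difference". Inputs: difference 1.8, SD 5.5, two-sided alpha 0.05, power 0.90, allocation 2:1. The synopsis expects 444 evaluable of 555 randomized, which is 1 − 444/555 = 20% loss.

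- Placebo n = (1 + 1/2) × (1.960 + 1.282)² × 5.5² / 1.8² = 1.5 × 10.51 × 30.25 / 3.24 ≈ 147.2, rounded up to 148.
- Active n = 2 × 148 = 296; total 444; 444 / 0.80 = 555.
- Power at 148 and 296 is 0.902 at alpha 0.05 and 0.901 at 0.0499 (normal approximation).

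The plan's figure reproduces. It uses only a mean difference and an SD; no mortality rate or Mann-Whitney probability enters.

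**3. Does the power carry over to the joint-rank endpoint?** The documents give no mortality, so the rates below are assumptions. The simulation used 4,000 runs per scenario, 148 versus 296 patients, a 1.8-point shift, SD 5.5, an unstratified Mann-Whitney test at 0.0499, and deaths ranked worst by time and independent of ALSFRS-R change.

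| Mortality placebo / active | Joint-rank power |
|---|---|
| 0% / 0% | 0.89 |
| 5% / 5% | 0.82 |
| 10% / 10% | 0.73 |
| 15% / 15% | 0.62 |
| 10% / 5% | 0.94 |
| 5% / 10% | 0.43 |

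These values are illustrative. In the trial, patients who die would still be ranked, so more than 444 could enter, and ventilation dependence is not modelled. They show that power depends on inputs the plan does not state, and that high but equal mortality lowers it.

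**4. Which design rules cover which endpoint.**

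- ALSFRS-R primary only: the 90% power (Protocol 9.2, SAP 4.3.1); futility at conditional power below 0.10 (SAP 5.1); the 0.40 to 0.90 zone for adding 150 patients (SAP 4.3.2 and 5.1).
- Secondary endpoints too: the 0.0001 interim boundary and the 0.0499 final level (Protocol 9.5, SAP 5.1). The DMC may also look at the first secondary endpoint for futility, and SAP 5.2 specifies how its ranks are formed after a sample-size increase.

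**5. Type I error.**

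- *Blinded choice.* Under no effect on any component, pooled deaths carry essentially no information about the treatment contrast. If the switch happens with probability p, final-analysis error is p × 0.0499 + (1 − p) × 0.0499 = 0.0499, near 5%.
- *Worst case.* Suppose both results are known and the better is chosen. The error is P(|Z₁| > c or |Z₂| > c) with c = z(1 − 0.0499/2) ≈ 1.961 and correlation ρ. This gives 7.8% at ρ = 0.80, 7.0% at 0.90 and 6.4% at 0.95. Lower correlations give more: 8.3% at 0.70 and 9.1% at 0.50. The documents state no correlation; high values are plausible because most patients would be ranked on ALSFRS-R change.

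**The case against.** The strongest reply is that the switch is tied to mortality, must precede lock, and would be made by people who do not know the results. SAP 4.1 keeps sponsor personnel and contractors working on the trial blinded for 48 weeks, with one unblinded monitor excepted. Unblinded efficacy results go only to an independent DMC and its statistical group. Deaths reach the sponsor as serious adverse events, so pooled mortality is visible without unblinding. This stands. A reader might infer that the plan's error rate is 6.4% to 7.8%, or that the decision would be informed by the interim results. The documents support neither reading.

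A reader might also infer that none of the interim design applies to the joint-rank endpoint. That is too strong, because the 0.0001 and 0.0499 levels are set for every secondary endpoint.

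Finally, the option has a rationale. The main analysis imputes missing ALSFRS-R scores under MAR, with no separate treatment of deaths; only a sensitivity analysis treats them separately. High mortality is where a joint-rank primary is most attractive, and under SAP 8.5 the joint-rank test cannot be confirmatory once Step 1 fails. So it would be wrong to say that deletion loses nothing.

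None of this supplies a threshold, a decision-maker or agreement with the protocol.

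**Conclusion.** The point holds as a conflict between confirmatory rules. One SAP sentence permits a change of primary that the protocol does not contain and that SAP 8.5 and 8.6.1 contradict, on a trigger no reader could verify.

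The error-rate consequence is probably small. It stays near 5% if the decision uses blinded pooled mortality; 6.4% to 7.8% is a ceiling that requires knowledge of both results, free choice between them, and correlations of 0.80 to 0.95. The more certain consequences are that the 90% power, the formal futility threshold and the promising-zone rule have no stated counterpart for the replacement endpoint, and that a positive result after a switch would be open to challenge.

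**What to change.** Delete the sentence from SAP 8.7.1. Keep ALSFRS-R change at Week 24 as the primary and the joint-rank test as Step 2. This changes one sentence; sample size, alpha and Step 1 stay as they are. The small cost is losing a confirmatory route for the joint-rank endpoint when Step 1 fails under high mortality.

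If the sponsor wants to keep that route, write it into both the protocol and the SAP with:

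- a numeric threshold on pooled, blinded mortality;
- a named decision-making role that is blinded to treatment and results;
- a fixed decision date, preferably before any unblinded interim;
- the testing order after a switch, including where ALSFRS-R change then stands;
- power, futility and sample-size rules for the joint-rank endpoint under stated mortality assumptions.

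This second route needs a protocol amendment and new design calculations.
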